## **8.2 Subject Identification and Replacement of Subjects**

Each subject will be assigned a unique subject identifier. This unique identifier will be on all case report form (CRF) pages. Subjects who do not receive at least one dose of tipifarnib will

be replaced. Subjects who do not have at least one post baseline disease assessment will be replaced.

### **8.3 Assignment to Treatment Groups**

All eligible subjects will receive tipifarnib treatment. Assignment to a high CXCR4/2 ratio or a low CXCR4/2 ratio cohort will be provided by the Sponsor based on the results of the testing of screening bone marrow samples at a central laboratory.

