Each cohort has a 2-stage design. Seven subjects will be enrolled in the first stage of each cohort. If at least one objective response is observed, the cohort will be expanded to enroll an additional 11 subjects in stage 2. The cohort will be considered positive if 4 or more responses are observed in the 18 subject cohort ([Figure 1](#)). Based on the absence of objective responses observed in the initial cohort of RAS mutant CMMML subjects, all enrolled subjects enrolled in amendment 3 cohorts 1-4 will have RAS wild type tumor status at study entry.

Only consented subjects who meet all eligibility criteria will be enrolled in the study. Screening evaluations will be completed within 4 weeks (28 days) of Cycle 1 Day 1. Any screening evaluation, including disease status, will need to be repeated if performed more than 4 weeks from Cycle 1 Day 1. Evaluations performed as part of the standard of care within 28 days of dosing but prior to consent, do not need to be repeated. By signing the consent form, study subjects agree to the collection of standard of care health information.

Subjects (amendment 3 cohorts 1-4) will receive tipifarnib administered at a dose of 400 mg, orally with food, bid for 21 days in 28 day cycles. Food intake is important for tipifarnib bioavailability. The relevance of food intake with tipifarnib administration should be highlighted to study subjects. Subjects may use proton pump inhibitors or H2 antagonists during the treatment portion of this study. However, subjects should be instructed to use antacids (magnesium or aluminum containing products) at least 2 hours before or after intake of oral study drug.

Stepwise 100 mg dose reductions to control treatment-related, treatment-emergent toxicities are indicated in the body of the study protocol. In the absence of unmanageable toxicities, subjects may continue to receive tipifarnib treatment until disease progression. In the absence of unmanageable toxicities, subjects may continue to receive tipifarnib treatment until disease progression. Provisions will be made for the continuation of study treatment in subjects whose disease has not progressed beyond the end of the study, e.g. a single patient treatment protocol.

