Disease assessments will be performed at screening, at the Day 25 visit ( $\pm$  5 days) performed during Cycles 2, 4, 6, 9 and every approximately 12 weeks thereafter (Cycles 12, 15, etc.), at the End of Treatment visit and during follow up. As part of the disease assessment at screening and at the Day 25 visit performed during Cycles 2, 4, 6 and 9, bone marrow evaluations will be conducted. Thereafter, bone marrow evaluations will occur during disease assessments in accordance with institutional standard practice. Hematologic assessments, including peripheral blood evaluations and review of transfusion requirements, will be performed at screening and at least monthly until disease progression.

Additional disease or hematologic assessments may be conducted if deemed necessary by the Investigator. The timing of the disease and hematologic assessments should be maintained as much as possible independently of potential treatment cycle delays.

Determination of disease response in subjects with MDS/MPN subjects will be performed by the Investigator according to the Myelodysplastic/Myeloproliferative International Working Group (MDS/MPN IWG) criteria ([Table 9](#)). Similarly, disease progression will also be determined based on the MDS/MPN IWG criteria ([Table 10](#)). Determination of disease response in subjects with AML will be performed by the Investigator according to the International Working Group criteria (Cheson 2003). Similarly, disease progression will also be determined based on the IWG criteria (Cheson 2003).

Upon disease progression, all subjects in the study will be followed approximately every 12 weeks for survival and the use of subsequent therapy until either death or 12 months after accrual of the study cohort has been completed, whichever occurs first. Information on survival and subsequent anticancer therapy may be collected by phone.

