## **9.7 Blinding**

This is an open label study with no placebo or comparators.

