- Perform serum chemistry laboratory tests (AST, ALT, total bilirubin, creatinine, potassium and calcium). Subjects are not required to be fasting.
- Perform coagulation tests (APTT, PT/INR)

The following evaluations and procedures will be performed within 72 hours prior to the first administration of study drug (Cycle 1 Day 1):

- Perform urine or serum pregnancy test for females of child-bearing potential only

Laboratory assessments may be repeated if values are borderline to inclusion level or may change due to best supportive care measures.

If the subject meets all eligibility criteria after the screening visit(s), the study site will request an assigned subject number and treatment assignment from the Sponsor or designee.

## 11.2 Day 1 of Cycle 1

The following assessments will be conducted before the first dose of tipifarnib on Day 1 of Cycle 1:

- Record concomitant medications

- Assessment of AEs
- Record subject weight
- Assess ECOG performance status.
- Symptom based physical examination
- Perform serum chemistry laboratory tests (AST, ALT, total bilirubin, creatinine, potassium and calcium). Subjects are not required to be fasting. Serum chemistry tests do not need to be repeated on Cycle 1 Day 1 if the screening laboratory tests were conducted within 72 hours prior to the first dose of tipifarnib.
- Perform hematology tests (hemoglobin, platelets, WBCs, neutrophils, neutrophil precursors, lymphocytes, monocytes and blasts). Hematology tests do not need to be repeated on Cycle 1 Day 1 if the screening hematology tests were conducted within 72 hours prior to the first dose of tipifarnib.
- Record any RBC, whole blood and platelet transfusions that were received between the screening visit and Cycle 1 Day 1.
- Collect serum and plasma samples for biomarker evaluation

Tipifarnib should always be administered with a meal. For convenience, subjects may receive only one dose of tipifarnib on Cycle 1 Day 1, with subjects self-administering the first dose of tipifarnib with food in the evening. Subjects will continue to self-administer tipifarnib twice a day (approximately every 12 hours, same time every morning and evening, with a meal). The interval between dosing should not be less than 6 hours.

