10.1 Definition of endpoints

Disease assessments other than bone marrow (hematology and quality of life evaluations) will be performed at screening, and at the Day 25 visit (\pm 5 days) performed during Cycles 2, 4, 6, 9 and every approximately 12 weeks thereafter (Cycles 9, 12, 15, etc.), at the End of Treatment visit and during Follow Up. Bone marrow evaluation will be performed as part of the disease assessment at screening and at the Day 25 visit (\pm 5 days) performed during Cycles 2, 4, 6 and 9. Thereafter, bone marrow evaluations will occur during disease assessments in accordance with institutional standard practice. Hematologic assessments, including peripheral blood evaluations and review of transfusion requirements, will be performed at screening and at least

monthly until disease progression. Additional disease or hematologic assessments may be conducted if deemed necessary by the Investigator.

For subjects with CMMI and MDS/MPN, determination of disease response will be performed by the Investigator according to the MDS/MPN IWG criteria (Protocol Table 9 and 10); Objective Response (OR) is achieved if the investigator indicates complete response, complete cytogenetic remission, partial remission, marrow response, or clinical benefit.

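### The plan indicates that sites learn each subject's high or low CXCR4/2 cohort before dosing, and nothing withholds it from the investigator who alone calls the response

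*Protocol*

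**What the plan says.** **Who assigns and who asks.** Protocol 8.1 has the CXCR4/2 ratio measured at a central laboratory on a screening marrow sample, and the Synopsis makes that sample a condition of assignment to a cohort. Section 8.3 states: "Assignment to a high CXCR4/2 ratio or a low CXCR4/2 ratio cohort will be provided by the Sponsor". In section 11.1, once a subject is found eligible, "the study site will request an assigned subject number and treatment assignment from the Sponsor or designee". Section 9.3 speaks only of a subject number, which the site must have before it can enrol or dose.

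**What differs between cohorts.** Section 8.3 states: "All eligible subjects will receive tipifarnib treatment". Section 8.1 gives one regimen: "Subjects (amendment 3 cohorts 1-4) will receive tipifarnib administered at a dose of 400 mg, orally with food". MDS/MPN and AML differ in response criteria and in the symptom questionnaire. Within a disease, no regimen, visit or assessment is tied to the ratio.

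**Who calls response.** Section 8.1 states: "Determination of disease response in subjects with MDS/MPN subjects will be performed by the Investigator"; the same rule applies to AML. SAP 10.1 takes that call as the primary endpoint: "Objective Response (OR) is achieved if the investigator indicates complete response, complete cytogenetic remission, partial remission, marrow response, or clinical benefit".

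**Masking.** Section 9.7 states: "This is an open label study with no placebo or comparators". Neither document mentions withholding the ratio, an independent response review, or a sensitivity analysis of response calls.

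**What investigators are told.** Section 8.1 reports that in the initial CMML cohort a high ratio was significantly associated with clinical benefit, and that amendment 3 is meant to test this prospectively.

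**The concern.** The person who judges response appears to know both the hypothesis and the marker value of the subject being judged. Open-label treatment is unavoidable when everyone receives the drug. Disclosure of the marker is not, because the site has no stated use for it.

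The main quantity at risk is the high-versus-low ORR comparison, not the single-arm test of each cohort against 10%. The cohorts are small and the rule turns on a few calls: at least 1 response in 7 to continue, and at least 4 in 18 to be positive. If borderline cases are read upward when the ratio is high, or downward when it is low, the two MDS/MPN cohorts could separate with no biological difference between them. SAP section 4 says AML enrolment was held and that the report will cover CMML and MDS/MPN only, so the point now bears mainly on those two cohorts.

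**Working it through.** **Step 1: is the category disclosed?** Section 8.3 does not name the recipient, so this is an inference.

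| Place | What it contributes |
|---|---|
| Synopsis | The marrow sample is needed for cohort assignment |
| 8.3, headed as treatment-group assignment | The Sponsor provides high or low |
| 11.1 | The site requests a subject number and a treatment assignment |
| 8.1, 8.3 | Same drug and regimen in all four cohorts |
| 9.3 | Mentions a subject number only |

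The site already knows the diagnosis, and the drug is the same for all. Within a disease, the ratio cohort is the only assignment left to pass on. Disclosure is the natural reading, and no text prevents it.

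**Step 2: reproduce the plan's own figures.** Inputs (Protocol 12.3, SAP 5.3.2): 7 then 11 subjects, continue if at least 1 of 7 responds, positive if at least 4 of 18 respond, null 10%, alternative 30%.

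P(positive | p) = Σ over x = 1 to 7 of P(Bin(7, p) = x) × P(Bin(11, p) ≥ 4 − x)

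- p = 0.10: 0.372 × 0.0896 + 0.124 × 0.3026 + 0.023 × 0.6862 + 0.0027 = 0.0893. Stated: 0.089.
- p = 0.30: 0.2471 × 0.6873 + 0.3177 × 0.8870 + 0.2269 × 0.9802 + 0.126 = 0.800. Stated: 80%.

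Both agree. In each line the last term is the chance of 4 or more responses in stage 1.

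**Step 3: over-calling in the high cohort only.** The documents give no error rates, so the rates o below are assumptions. True ORR is 10% in both cohorts, the low cohort is called correctly, and the cohorts are independent. The apparent high-cohort rate is 0.10 + 0.90 × o.

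- High only = P(high positive) × (1 − 0.0893)
- Low only = 0.0893 × (1 − P(high positive))

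| o | Apparent ORR, high | P(high positive) | High positive, low not | Low positive, high not |
|---|---|---|---|---|
| 0 | 0.100 | 0.089 | 0.081 | 0.081 |
| 2.5% | 0.1225 | 0.156 | 0.142 | 0.075 |
| 5% | 0.145 | 0.238 | 0.217 | 0.068 |
| 10% | 0.190 | 0.424 | 0.386 | 0.051 |

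In subjects, o = 5% is 18 × 0.90 × 0.05 = 0.8 extra responses in a full cohort, and o = 10% is 1.6.

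**Step 4: isolate the marker-dependent part.** Suppose the same over-calling happened in both cohorts, which withholding the label would not prevent. P(high positive, low not) would then be 0.238 × (1 − 0.238) = 0.181 at 5% and 0.424 × (1 − 0.424) = 0.244 at 10%. The mirror-image pattern would be equally likely, so neither direction would be favoured. With over-calling tied to the marker, the favoured pattern is 0.217 / 0.068 = 3.2 times as likely as its mirror image at 5%, and about 7.5 times at 10%. That tilt is what withholding the label can remove.

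**Step 5: under-calling in the low cohort.** With true ORR 30% in both cohorts, missing 10% or 20% of low-cohort responders gives an apparent rate of 0.27 or 0.24. The low cohort's chance of being positive falls from 0.800 to 0.720 or 0.621. The pattern of high positive with low not rises from 0.160 to 0.224 or 0.303.

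**Step 6: how long masking would last.** At p = 0.10 a cohort stops at stage 1 with probability 0.9^7 = 0.478 (stated 0.48). If both cohorts are at 10%, at least one stops with probability 1 − (1 − 0.478)² = 0.73.

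**The case against.** The strongest reply is that no sentence says the category reaches the site. Section 8.3 names no recipient, section 11.1 asks for a treatment assignment rather than a ratio result, and section 9.3 needs only a number. This stands as a limit: disclosure is a strong inference, not a stated fact. It does not clear the plan, because nothing withholds the label.

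Second, each cohort's verdict is a single-arm comparison with 10%, where open-label over-calling can occur whether or not the ratio is known. This also stands. The 0.238 and 0.424 chances of a positive high cohort apply to any over-calling and should not be credited to marker knowledge. The SAP plans no formal high-versus-low test of ORR; it reports ORR by subgroup. Its hazard ratio and log-rank comparison by ratio sit in the survival section, and death is not open to response-call bias.

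Third, how far calls can be swayed is unknown. The response-criteria tables are redacted, so it cannot be said here that the clinical benefit category is soft. There are safeguards: a CR or PR on marrow requires a repeat aspirate a month later (Protocol 11.5), and assessments follow a fixed cycle schedule.

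A reader might also infer that amendment 3 gave up an earlier protection, because RAS status in the initial CMML cohort was stratified retrospectively. The documents do not support this. The phrase says when the grouping was applied; nothing says investigators were unaware of RAS status. Prospective classification is also needed now, since each ratio cohort has its own quota.

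**Conclusion.** The point holds as an exposure to bias in the high-versus-low ORR comparison, now mainly in the two MDS/MPN cohorts. It rests on reading 8.3, 11.1 and the Synopsis together, and on the absence of any text that withholds the marker or adds independent review. The documents do not show that biased calls occurred.

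Under the assumed 5% and 10% over-call rates in the high cohort, true ORR 10% in both cohorts and independent cohorts, the chance of a misleading high-only result goes from 0.081 to 0.217 and 0.386. One or two calls per cohort are enough. The stronger reading, that knowledge of the ratio by itself undermines each cohort's test against 10%, goes too far: much of that risk comes from open-label investigator assessment and would remain. The comparison is descriptive but is the reason for amendment 3, and the protection is cheap, so the change should be made.

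**What to change.** In Protocol 8.3 and 11.1, state that the site receives only the subject number and whether a slot is available. State also that the numeric ratio and the high or low category stay with the central laboratory and a restricted sponsor function until that subject's best response is entered and locked. Bring 9.3 and 9.7 into line, so that open label clearly refers to the drug and not to the marker. Where a category has already been released, a re-read of response from existing records by someone unaware of the ratio is a fallback.

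The cost is protocol and laboratory-manual wording and restricted access to the assignment file; the fallback would add reader time. Sample size, decision rule, alpha (0.089), power (0.80), visits and treatment are unchanged.

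The limitation is material. Once one ratio cohort closes or pauses, later entrants must belong to the other, so masking is then only partial. With ORR 10% in both cohorts, at least one stops at stage 1 with probability about 0.73. The protection is most secure for calls made while both cohorts are open, which includes many stage 1 calls.

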### **8.4 Removal of Subjects from Treatment or Assessment**

Subjects may withdraw their consent to participate in this study at any time without prejudice. The Investigator must withdraw from the study any subject who requests to be withdrawn. A subject's participation in the study may also be discontinued at any time at the discretion of the Investigator and in accordance with his/her clinical judgment. Every effort should be made to complete, whenever possible, the tests and evaluations listed for the End of Treatment visit. The Sponsor must be notified of all subject withdrawals as soon as possible. The Sponsor also reserves the right to discontinue the study at any time for either clinical research or administrative reasons and to discontinue participation by an individual Investigator or site for poor enrollment or noncompliance.

Overall, the reasons for which the Investigator or Kura Oncology may withdraw a subject from study treatment include, but are not limited to, the following:

- Subject experiences disease progression
- Subject experiences unacceptable toxicity
- Subject experiences toxicity that is deemed by the Investigator to be no longer safe for the subject to continue therapy
- Subject requests to withdraw from the study treatment
- Subject requires or has taken medication prohibited by the protocol
- Subject is unwilling or unable to comply with the study requirements
- Subject withdraws consent to collect health information
- Subject was erroneously admitted into the study or does not meet entry criteria
- Subject is lost to follow-up
- Subject becomes pregnant

Subjects will return for an End of Treatment visit within approximately 30 days after the last administration of the study drug (or sooner if another anticancer therapy is to be initiated). If a subject fails to return for scheduled visits, a documented effort must be made to determine the reason. If the subject cannot be reached by telephone after 2 attempts, a certified letter should be sent to the subject (or the subject's legally authorized representative, if appropriate) requesting contact with the Investigator. This information should be recorded in the study records.

Prior to enrollment into the study, the Investigator or designee must explain to each subject, that the subject's protected health information obtained during the study may be shared with the study Sponsor, regulatory agencies, and Institutional Review Board/Independent Ethics Committee (IRB/IEC) in order to analyze and evaluate study results. It is the Investigator's (or designee's) responsibility to obtain written permission to use protected health information per country-specific regulations, such as Health Information Portability and Accountability Act (HIPAA) in the United States, from each subject, or if appropriate, the subject's legally authorized representative. If permission to use protected health information is withdrawn, it is the Investigator's responsibility to obtain a written request, to ensure that no further data will be collected from the subject and the subject will be removed from the study.

## **8.5 Premature Discontinuation of the Trial**

This study may be discontinued prematurely in the event of any of the following:

- New information leading to a judgment of unfavorable risk-benefit of tipifarnib becomes available, e.g. evidence of inefficacy of tipifarnib in subjects with CMML, occurrence of significant previously unknown adverse reactions or unexpectedly high intensity or incidence of previously known adverse reactions, or other unfavorable safety findings in the CMML patient population. Evidence of inefficacy may arise from this study or from other trials; unfavorable safety findings may arise from clinical or non-clinical examinations, e.g. toxicology.
- Sponsor's decision that continuation of the study is unjustifiable for medical or ethical reasons.
- Poor enrollment of subjects making completion of the study within an acceptable time frame unlikely.
- Discontinuation of development of tipifarnib by the Sponsor.
- Request by a Health Authority.

Health Authorities and IRBs/IECs will be informed about the discontinuation of the study in accordance with applicable regulations. In the case of premature discontinuation of the study, the investigations scheduled for the End of Treatment assessment should be performed and the appropriate CRF section completed.

## **8.6 Definition of End of Study**

For administrative and safety reporting purposes, the end of this clinical study is defined as the day when the last remaining study subject in the study completes the last follow-up assessment no later than 12 months after the last study subject is enrolled in the study. Provisions will be made for the continuation of study treatment in subjects whose disease has not progressed beyond the end of the study, e.g. a single patient treatment protocol.

## **9 TREATMENTS**

Subjects will receive tipifarnib as monotherapy in this study. In the absence of unmanageable toxicities, subjects may continue to receive tipifarnib treatment until disease progression. If a complete response is observed, therapy with tipifarnib will be maintained for at least 6 months beyond the start of response.

Kura Oncology, Inc. or its designee will provide the study site with a supply of tipifarnib sufficient for the completion of the study.

All study subjects will be also eligible to receive best supportive care (BSC) defined as any standard supportive measures that are not considered a primary treatment of the disease under study. BSC will be provided by the study sites.

### **9.1 Investigational Product**

Tipifarnib is a small molecule being developed as a potent, selective inhibitor of farnesyltransferase for the treatment of cancer and other malignancies.

